11.2. Efficacy

Change in pain score will be calculated by subtracting the patient's week 4 score from his or her baseline value prior to treatment initiation. Change in scores will be summarized using means and standard deviations provided the resulting distribution is symmetric, otherwise medians and interquartile ranges will be used. Provided the resulting distribution of pain scores is roughly normal, we will use a two-sample t-test to compare the QUELL FLEX and sham groups. Previous studies suggest that the average pain value at baseline is at least 4 on the 0-10 numerical rating scale with a standard deviation of the original pain value expected to fall in the range of 1-1.5 in this patient population. As such, a conservative estimate of the standard deviation would be approximately 20%. With 19 patients in each arm and under these assumptions, we will have the ability to detect a change of 2.0 points in the QUELL FLEX group with power of 0.90. If the change score distribution is highly skewed, Wilcoxon's signed rank test will be utilized instead.

To account for ~20% dropout rate, we will add 4 subjects to each arm for a total of 23 subjects per arm. We included a dropout rate of ~20% based on previous studies with this device. We will run a sensitivity analysis to determine if the drop-out rate in either arm had an impact on the trial results.

A 20% reduction in pain has been previously determined to be a clinically meaningful improvement, we will report the number and percent of patients from each group who achieve this benchmark.

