2.2. Primary Objective

The primary objective is to determine the difference in the Numerical Pain Scale score between the baseline screening call and at week 4 in the treatment group compared with the same difference in the placebo or sham group.

The Numerical Pain Scale is an 11-point scale (0-10) that includes guides to assist in the

determination of the pain level.

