6.4 Randomization and Blinding

Randomization would be done in blocks of 4 (e.g. 2 placebo and 2 treatment assignments) assigned at random at the beginning of the study for each 4 patients enrolled in the study consecutively. This ensures that it is not possible to predict the arm assignment of patients as we unblind them in groups of 4 at the conclusion of each patient's participation in the study.

Blinding keys, including the arm assignment of the patient, will be sealed in envelopes and not opened until unblinding occurs for the 4-patient-block.

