10. At the conclusion of the 4-week experimental arm, all patients will be shipped a new QUELL FLEX device for use in the 4-week open label phase. This one will be functional. The experimental QUELL FLEX devices will be returned in the same shipping box to the study team. Study staff will administer the SF-36 Quality of Life questionnaire.
11. In the 4-week open label phase, patients will continue to use the device with the electrodes in the same position. Weekly pain scores will be documented as before as well as the SF-36 Quality of Life questionnaire at the conclusion of the 4-week open label period.
12. At the conclusion of the 4-week open label period for the 4-patient block, blinding will be unsealed and reported to the patients. They will then have the opportunity to keep the functional QUELL FLEX if they wish.
13. Four and eight weeks after the completion of the open label phase, patients will be called for a wellness check and asked to rate their pain again.
14. Adverse Events will be monitored and documented weekly.

6.5.1.2. Treatment follow-up:

Patients will be contacted by Zoom weekly during the experimental and open-label phases to check in on them, and will be asked weekly to report their pain score. At the conclusion of the experimental phase and at the end of the study, patients will be asked again to complete the Short Form-36 Health Inventory (SF-36).

[figure not shown]
TENS for Neuropathic Pain in NMOSD

Principal Investigator: [name], PhD

Patient-Reported Outcomes

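### Section 11.2 lets the observed distribution choose the primary test and, separately, the summary measure, with no cut-off and no requirement that the choice be made blinded

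*Combined protocol and SAP*

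**What the plan says.** Section 2.2 sets the primary contrast between arms: the baseline-to-week-4 difference "at week 4 in the treatment group compared with the same difference in the placebo or sham group". Section 11.2 then attaches three data-dependent conditions to its analysis.

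- Main test: "Provided the resulting distribution of pain scores is roughly normal, we will use a two-sample t-test to compare the QUELL FLEX and sham groups".
- Fallback: "If the change score distribution is highly skewed, Wilcoxon's signed rank test will be utilized instead".
- Summary: means and standard deviations are used "provided the resulting distribution is symmetric, otherwise medians and interquartile ranges will be used".

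None of the three comes with a numerical criterion, a named diagnostic, or a statement of whether the arms are pooled or examined separately.

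On blinding, Section 6.4 describes participants' assignments "as we unblind them in groups of 4", with the keys "not opened until unblinding occurs for the 4-patient-block". Section 6.5.1.1, step 12, gives the timing: "At the conclusion of the 4-week open label period for the 4-patient block, blinding will be unsealed and reported to the patients". No section says who examines the distribution, when, or with what knowledge of the arms.

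**The concern.** A primary analysis should be fixed before anyone can see which version of it gives the better answer. Here the test depends on a judgement about the week-4 data, and the text gives no standard for that judgement. One analyst may call a distribution close enough to normal and run the t-test. Another may call the same distribution strongly skewed and run a rank test. Both have followed the plan.

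The question answered also changes with the choice. The power statement in 11.2 is about a 2.0-point change, which is a mean in points. A rank test with medians and interquartile ranges addresses something else. The plan names no primary effect estimate or confidence interval that would hold the report to one measure.

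The blinding arrangements do not protect the choice, because nothing ties it to a moment before arms are known.

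**Working it through.** **Inputs from the documents.** 46 patients, 23 per arm, 19 evaluable per arm; difference 2.0 points; stated power 0.90; SD of the original pain value 1 to 1.5, then a working SD of about 20% with its base not stated (all 11.2, with the total in 6.2). Block size 4 (6.4). Alpha and sidedness are not stated.

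**The plan's own figure.** The power of 0.90 is for a mean-based comparison. The noncentrality is 2.0 / (SD × √(2/19)). If 20% means 20% of the 10-point scale, SD = 2.0 and the noncentrality is 3.08. Two-sided 0.05 (assumed) then gives 0.869 by the normal approximation and 0.851 by the t distribution. SD = 1.5 gives 0.984 and 0.979. A two-sided 0.90 needs an SD of about 1.85 to 1.90. So 0.90 cannot be tied to one documented set of inputs. What matters here is that no power is stated for the fallback.

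**Timing.** 46 / 4 = 11.5, so there are 11 full blocks and one half block. A block is opened after its open-label phase, so its own week-4 scores are already recorded. The full distribution exists only when the last patient reaches week 4. By then earlier blocks may be open; how many depends on accrual, which is not given.

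**Simulation.** All settings are assumptions: two-sided 0.05; changes rounded to whole points; normal or strongly skewed (gamma, shape 1); SD 1.5 or 2.0; 20,000 trials per setting. A two-sample rank-sum test stands in for the named signed rank test, because the latter does not compare two independent arms. The skewness rule uses pooled changes centred by arm and switches to rank-sum above a cut-off of 0.5, 1 or 2. Results at 19 per arm, as the percentage of trials significant:

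| Changes, SD | True difference | t-test | Rank-sum | Rule 0.5 / 1 / 2 | More favourable test | Tests disagree |
|---|---|---|---|---|---|---|
| Normal, 1.5 | 0 | 5.14 | 4.98 | 5.40 / 5.24 / 5.15 | 5.90 | 1.68 |
| Normal, 2.0 | 0 | 4.88 | 4.57 | 5.10 / 4.94 / 4.88 | 5.50 | 1.56 |
| Skewed, 1.5 | 0 | 4.56 | 4.76 | 4.78 / 5.12 / 5.13 | 6.14 | 2.96 |
| Skewed, 2.0 | 0 | 4.92 | 4.89 | 5.03 / 5.54 / 5.36 | 6.46 | 3.12 |
| Normal, 2.0 | 2.0 | 84.29 | 82.19 | 84.41 / 84.32 / 84.29 | 85.42 | 4.36 |
| Skewed, 2.0 | 2.0 | 83.48 | 93.73 | 93.83 / 93.43 / 87.42 | 94.05 | 10.89 |

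The Monte Carlo standard error near 5% is √(0.05 × 0.95 / 20,000) = 0.15 percentage points. At 23 per arm with no true difference, the fixed rules give 4.86 to 5.48% and the more favourable test 5.66 to 6.80%. In a separate set of 8,000 null trials per scenario (19 per arm, whole-number 0-10 scores), switching on a Shapiro-Wilk test gave 4.6 to 5.1%.

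**How far the missing cut-off decides the test.** At 19 per arm, absolute skewness exceeds 0.5, 1 and 2 in about 18%, 1% and almost 0% of trials with normal changes. With skewed changes at SD 2.0 the shares are 97%, 76% and 17%.

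**Limit of the stand-in.** If the signed rank test were run as named on the QUELL FLEX arm's own changes (n = 19), with no difference from sham but an assumed 1-point improvement in both arms, it would be significant in 54% (SD 2.0) to 77% (SD 1.5) of 4,000 simulated trials per setting. The near-5% results therefore apply only once the fallback is a two-sample test.

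**The case against.** Several stronger readings are tempting, and the documents do not support them.

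- *Two different variables are checked.* The t-test sentence speaks of pain scores and the fallback of change scores. But the paragraph opens by defining the change, and the next two sentences both refer to the resulting distribution. It reads most naturally as being about one variable, the change.
- *Data between the two conditions have no test.* The fallback replaces the t-test only under strong skew, so the t-test can be read as the default otherwise.
- *The choice will be made with arms known.* The text does not say so. Blinded checking is not required, but neither is it excluded.
- *Type I error is badly inflated.* The 5.5 to 6.8% belongs to running both tests and reporting the better one. The plan states a vague rule and does not license that. A rule fixed at any of the cut-offs tried and followed honestly stays near 5%.

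It is also fair to say that the fallback is named in advance, that the mean-or-median rule is descriptive while Section 2.2 fixes the contrast, and that naming a signed rank test for two independent arms is the more consequential defect in the same sentence.

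What stands is that the threshold between the tests is missing, the summary switches on its own undefined condition, and nothing places the decision before arms are known. Section 2.2 fixes which groups and times are compared, but not whether the result is a mean or a median difference. Correcting the name of the rank test would leave the choice of test to the data.

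**Conclusion.** The point holds in moderate form and should be changed. The primary p-value and the measure reported with it are not fixed in advance. Under the assumed distributions, the t-test and rank-sum test disagree on significance in 1.6 to 3.5% of null trials across 19 and 23 per arm. At a 2.0-point difference with SD 2.0 and 19 per arm, they disagree in 4.4% (normal) to 10.9% (skewed). Selective choice would raise type I error by roughly 0.5 to 1.8 percentage points above 5%. These sizes rest on assumed distribution shapes, a two-sided 0.05 level and a rank-sum test in place of the one named; none of these comes from the documents. Nothing in the plan shows an intention to choose by result. The fault is that the text would not prevent it or reveal it.

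**What to change.** In Section 11.2, delete the distributional conditions on both the test and the summary. Name one mean-based between-arm comparison of the baseline-to-week-4 change, for example the two-sample t-test already there, as the primary analysis whatever the distribution looks like. Report it as a mean difference with a 95% CI, and state alpha and sidedness. Keep a two-sample rank-sum test, not the signed rank test, as a labelled sensitivity analysis that cannot replace the primary result. Medians and interquartile ranges may be shown as extra description. Adopt the wording before the first block is opened or, failing that, before any review of outcomes by arm.

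The cost is wording only, with no added patients, visits or data. The downside is lost power if changes are strongly skewed. In the skewed settings above at 19 per arm and a 2.0-point shift, the t-test has 83.5% against 93.7% for rank-sum at SD 2.0, and 96.8% against 99.5% at SD 1.5. With normal changes at SD 2.0 the t-test is slightly ahead, 84.3% against 82.2%.

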4.2.3. Data on Quell Relief

In a study for Quell TENS on back pain, the following results were reported:

“After six weeks, those in the Experimental group reported lower “worst” pain scores and less overall interference than those in the Control group ($p<0.025$). After three months those assigned to the Experimental group (hfTENS device) reported significantly less pain (worst, least, average, now) than those in the Control condition ($p<0.01$; Table 3). Pre-post comparisons on average pain intensity on the BPI showed significant groups differences (Experimental=1.24; Control=-0.03; $t=2.74$; $p<0.01$) with 31.0% of the Experimental group showing ≥ 2.0 differences vs. 12.9% among the Control group. Those in the Experimental group also reported less overall pain-related interference (general activity, mood, walking ability, work, relation with others, sleep, and enjoyment of life) compared with the Control group ($p<0.025$). Also, subjects assigned to use the hfTENS reported reduced pain catastrophizing scores compared with the Controls ($p<0.025$). No differences were noted between groups on the self-report questionnaires assessing disability (PDI) and anxiety and depression (HADS). Both groups demonstrated a reduction in the use of prescription pain medication, but no differences were found between groups.”

TENS for Neuropathic Pain in NMOSD

Principal Investigator: [name], PhD

5. Patient Population

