5.1. Inclusion Criteria

- 5.1.1. Men and women 18 years of age or older diagnosed with NMOSD per the 2015 NMOSD criteria
- 5.1.2. Patients must be positive for the aquaporin-4 antibody in serum
- 5.1.3. Presence of persistent neuropathic pain (≥ 3 months) rated at a level of 4 or higher on the Numerical Pain Scale
- 5.1.4. Patients must be stable in their disease, such that they have had no spinal cord relapses within 6 months prior to enrollment
- 5.1.5. Patients must be on a stable medication regimen that may include anti-epileptic, antidepressant, or non-steroidal anti-inflammatory medications, with no adjustments to the regimen within 30 days of enrollment
- 5.1.6. Pain must be localized to a spinal cord lesion
- 5.1.7. Patient understands the study regimen, its requirements, risks, and discomforts, and is able and willing to sign an informed consent form
- 5.1.8. Patients must own and be able to operate an iOS or Android smartphone with internet connection

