6.8.2. Withdrawal from Study

The reasons for withdrawal from the study include:

- Subject withdraws consent for follow-up.
- Subject is lost to follow-up.
- Study is terminated for any reason.

TENS for Neuropathic Pain in NMOSD

Principal Investigator: [name], PhD

7. Table 3: Patient Event Calendar

Phase	Baseline Screening/Consent	Experimental (Weeks)				Open Label (Weeks)				Follow-up (weeks)	
Time Point (days)	Within 2 weeks	1	2	3	4	5	6	7	8	12	16
Exam/Tests *	Consent, MRI review, Q [#]	AE and weekly pain score assessment, Q				AE and weekly pain score assessment, Q				AE and pain score assessment	AE and pain score assessment

#Q: Questionnaire (SF-36)

TENS for Neuropathic Pain in NMOSD

Principal Investigator: [name], PhD

8. Adverse Events

In over 4000 patients treated and reported to the FDA for approval, published and in-press studies, no significant adverse events have been reported with Scrambler and related TENS units.

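### The primary change-score t-test is valid but leaves collected baseline pain unused as a covariate; ANCOVA would cost at most about 3% of variance and plausibly save 6–28%, and the signed rank fallback does not compare the arms

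*Combined protocol and SAP*

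**What the plan says.** Section 11.2 defines the outcome by subtraction: "Change in pain score will be calculated by subtracting the patient's week 4 score from his or her baseline value prior to treatment initiation". If the distribution is roughly normal, "we will use a two-sample t-test to compare the QUELL FLEX and sham groups". Otherwise, "If the change score distribution is highly skewed, Wilcoxon's signed rank test will be utilized instead".

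No covariate model for the arm comparison appears anywhere in the document. The only regression, in Section 11.3, relates change in pain to change in SF-36.

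Section 11.2 bases power of 0.90 for 2.0 points on 19 patients per arm, then enlarges the sample: "To account for ~20% dropout rate, we will add 4 subjects to each arm". It gives a baseline SD of 1 to 1.5 and a planning SD of roughly 20% with no stated base. It gives no week-4 SD, SD of change, baseline to week-4 correlation, alpha or sidedness.

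Baseline pain is collected before device start (Section 6.5.1.1, item 1). Entry requires persistent neuropathic pain "rated at a level of 4 or higher on the Numerical Pain Scale" (Section 5.1.3).

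**The concern.** A change score assumes that each extra point of baseline pain carries through as a full extra point at week 4. The true slope is usually below 1, because patients who enter with high scores tend to drift back towards the mean. The change-score comparison then carries noise that the baseline rating could remove.

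With about 19 completers per arm, this affects the width of the confidence interval. It affects power only if the true difference is well below the planned 2.0 points. The back-pain study of a Quell device quoted in Section 4.2.3 shows that a smaller difference is possible. It reports "significant groups differences (Experimental=1.24; Control=-0.03", a gap of 1.24 − (−0.03) = 1.27 points.

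The fallback is a separate matter. A signed rank test asks whether one set of changes, or paired differences, is centred on zero. It does not answer the primary question of whether change differs between arms.

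**Working it through.** **Inputs.** From Section 11.2: n = 19 per arm, baseline SD s = 1 to 1.5, planned difference 2.0. From Section 4.2.3: 1.27 as an example of a smaller difference. Assumed, because the documents do not give them: correlation ρ = 0.3, 0.5, 0.7; k = SD(week 4)/SD(baseline); two-sided alpha 0.05.

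**The plan's own figure.** It cannot be pinned down, because alpha, sidedness and the base of the 20% are missing. If 20% means 2.0 points (20% of a 10-point scale), t-test power with 19 per arm is 0.85 two-sided at 0.05 and 0.92 one-sided. Power of 0.90 two-sided needs an SD of change of about 1.85.

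**Formulas.**
- Change score: Var = s²(1 + k² − 2ρk)
- ANCOVA residual: Var = k²s²(1 − ρ²)
- The first minus the second is s²(1 − ρk)². Before the slope is estimated, ANCOVA therefore never has the larger variance, and the two are equal only when the slope ρk is 1.
- Estimating the slope costs a factor 1 + 1/(2n − 4) = 1 + 1/34 = 1.029 on average. This sets the ceiling of about 3% on the loss, whatever ρ and k are.

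**Variance ratio, ANCOVA over change score, including the 1.029.** Example for k = 1, ρ = 0.3: 0.91 × 1.029 / 1.40 = 0.669.

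| k | ρ = 0.3 | ρ = 0.5 | ρ = 0.7 |
|---|---|---|---|
| 1 | 0.669 | 0.772 | 0.875 |
| 1.25 | 0.808 | 0.919 | 1.010 |
| 1.5 | 0.897 | 0.993 | 1.027 |

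**Which k is plausible here.** A floor of 4 at entry narrows the baseline distribution but not the week-4 one. This was simulated with latent normal pain of (mean, SD) (5, 1.5), (5, 2), (6, 1.5) and (4.5, 2), rounded to 0–10 and kept if baseline was 4 or more. Mean change was 0.5 on sham and 2.5 on active, with 20,000 trials per setting. The baseline SD came out at 1.2 to 1.5 and k at roughly 1.1 to 1.4. Variance savings were 20–28%, 13–19% and 6–11% for latent ρ of 0.3, 0.5 and 0.7. The two estimators had the same mean to within 0.003 points.

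**95% CI half-width, s = 1.5, k = 1.** 1.17 falls to 0.96 (ρ = 0.3), 0.99 to 0.87 (0.5) and 0.76 to 0.72 (0.7).

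**Power (noncentral t), change score then ANCOVA.**

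| Difference | s | k | ρ = 0.3 | ρ = 0.5 | ρ = 0.7 |
|---|---|---|---|---|---|
| 2.0 | 1.5 | 1 | 0.92, 0.98 | 0.98, 0.995 | both above 0.99 |
| 1.27 | 1.5 | 1 | 0.57, 0.75 | 0.72, 0.82 | 0.91, 0.94 |
| 1.27 | 1.5 | 1.2 | 0.49, 0.59 | 0.63, 0.67 | 0.83, 0.83 |
| 1.27 | 1 | 1 | 0.90, 0.98 | 0.97, 0.99 | both above 0.99 |

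**Which rating is the baseline.** Section 2.2 measures change "between the baseline screening call and at week 4", and Section 3.1 refers to a baseline or screening visit. Section 6.5.1.1 and Section 11.2 use a value taken before treatment starts. The event calendar has one pre-treatment column, "Baseline Screening/Consent", whose cell lists consent, MRI review and SF-36 but no pain score. Section 10.2 describes an intake phone call and a separate Zoom consent call, and Section 6.5.1.1 adds Zoom training. The calendar therefore does not settle which rating enters the analysis.

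**The case against.** The strongest reply is that nothing is wrong with the primary test. The objective and hypothesis are framed as a difference in change, the t-test on change answers exactly that, and ANCOVA is a preference. This stands as far as validity goes. A reader might infer bias or an inflated error rate from the missing adjustment; under randomisation the documents give no support for either.

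A second reply is that the gain is easily overstated, and this also stands. A saving near 60% follows from the formulas only if the week-4 SD is two-thirds of the baseline SD. The entry floor pushes the ratio the other way, so that figure should not be expected here. Even the equal-SD range of 33–12% is above what the simulated entry rule gives. The rise in power from 0.57 to 0.75 belongs to one corner: SD 1.5, equal SDs, correlation 0.3.

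Third, the 1.27-point example comes from back pain, measured on the BPI against a control condition. It is not week-4 Numerical Pain Scale against sham in NMOSD. It illustrates a smaller difference and does not predict one.

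Fourth, the fallback could be repaired with a rank-sum test and no ANCOVA. That is so; it is a separate fault and adds no weight to the efficiency argument.

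What remains is the asymmetry: a plausible saving of 6–28% against an expected loss of at most about 3%, using data already collected.

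**Conclusion.** The point holds as a recommended improvement in precision. It does not correct an invalid primary test. The 3% ceiling on the loss depends only on 19 completers per arm and the usual linear model. The 6–28% saving depends on an assumed correlation of 0.3 to 0.7 and on the simulated effect of the entry floor; it shrinks to about nil if week-4 pain is 1.5 times as variable as baseline.

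At 2.0 points with equal SDs of 1.5 or less, the planned test already has power of 0.92 or more, so the benefit there is mainly a tighter interval. A reader might infer that the trial is underpowered because of the change score. The documents do not show this, since the SD of change, alpha and sidedness are not stated.

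The signed rank fallback is a definite fault: as named, it does not test the primary hypothesis. The baseline rating also needs a single definition, whichever model is used.

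**What to change.** In Section 11.2:

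1. Make the primary analysis an ANCOVA of the week-4 Numerical Pain Scale score with arm as factor and baseline score as covariate. Report the adjusted difference with its 95% CI. Keep the change-score t-test as supportive.
2. Replace the signed rank test with a method that compares the arms: a rank-sum test on change, or a rank ANCOVA to match the primary model (regress ranked week-4 score on ranked baseline, then compare residuals between arms). A rank method gives no difference in pain points, so still report the adjusted difference.
3. State which single pre-treatment rating is the baseline, and use the same term in Sections 2.2, 3.1, 6.5.1.1 and 11.2 and in the calendar.

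Settle these before outcomes are examined by arm. Section 6.4 unblinds in blocks of 4 as patients finish, so the change should come early.

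Cost: wording only, with no new data or visits. The statistical price is one degree of freedom and, at worst, about 3% of variance.

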2.3. Secondary

Six secondary objectives are intended to collect additional information about the potential benefit of QUELL FLEX:

- A. The difference in pain scores at the end of the open label phase compared to the end of the initial blinded phase.
- B. A change in the “worst” pain score in the treatment arm vs. the sham arm between the baseline screening call and week 4; and the change in the “worst” pain from baseline to week 8 for all subjects.
- C. A change in the “average” pain score in the treatment arm vs. the sham arm between the baseline screening call and week 4; and the change in the “average” pain from baseline to week 8 for all subjects.
- D. The number of patients who withdraw because of poor compliance. We expect a higher withdrawal and non-compliance rate in the sham group.
- E. Quality of life surveys will be conducted before and after the treatment phase and at the end of the study to determine if the QUELL FLEX treatment impacts overall quality of life.
- F. Reduction in pain medication use over the course of the study.

TENS for Neuropathic Pain in NMOSD

Principal Investigator: [name], PhD

3. Hypotheses

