6.8. Discontinuation and Withdrawal of Subjects

All patients who initiate protocol intervention will be included in the overall evaluation of tolerability and acceptability (intent-to-treat analysis). All reasons for discontinuation of therapy will be clearly documented in the record.

Unless the subject refuses, follow-up will continue for the planned duration following the study intervention.

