6.8.1. Discontinuation of Intervention

The reasons for discontinuation of protocol treatment include:

- Non-compliance with the study protocol; including, but not limited to not using the device more than 75% of the study duration.
- Unacceptable major reaction to electrical stimulation or other major adverse events
- Intercurrent illness or condition that would, in the judgment of the treating investigator, affect assessment of clinical status to a significant degree or require discontinuation of study intervention.
- At subject's own request. Note: The reason for discontinuation from the study must be documented. The patients will be included in the overall evaluation of tolerability and acceptability (intent-to-treat analysis) if any protocol intervention was administered prior to withdrawal.
- Study is closed or cancelled for any reason.

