11.4. Reporting and Exclusions

Patients who sign a consent form, but do not initiate protocol intervention for any reason (e.g., patients who are screen failures), will be replaced and will not count towards our accrual goal.

TENS for Neuropathic Pain in NMOSD

Principal Investigator: [name], PhD

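### The primary test in 11.2, an unadjusted t-test on baseline-to-week-4 change, leaves out the baseline covariate and the week 1-3 scores, which costs precision and gives no protection if week-4 scores are missing for reasons related to pain

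*Combined protocol and SAP*

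**What the plan says.** Section 11.2 defines change as baseline minus week 4 and, if the distribution is roughly normal, "we will use a two-sample t-test to compare the QUELL FLEX and sham groups". If change is highly skewed, it switches to Wilcoxon's signed rank test. No covariate is named, and there is no efficacy analysis set and no rule for a missing week-4 score.

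On dropout, 11.2 allows for about 20% ("we will add 4 subjects to each arm for a total of 23 subjects per arm") and promises a check: "We will run a sensitivity analysis to determine if the drop-out rate in either arm had an impact on the trial results". It gives no method for that check. Objective D in 2.3 reads: "The number of patients who withdraw because of poor compliance. We expect a higher withdrawal and non-compliance rate in the sham group".

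On who is analysed, 6.8 says that patients who start the intervention "will be included in the overall evaluation of tolerability and acceptability (intent-to-treat analysis". It does not mention efficacy. Section 11.4 deals only with consented patients who "do not initiate protocol intervention for any reason (e.g., patients who are screen failures), will be replaced". Section 6.8.1 lists as a reason for stopping the intervention "Non-compliance with the study protocol; including, but not limited to not using the device more than 75% of the study duration". Section 6.8.2 does not list non-compliance as a reason for leaving the study, and 6.8 adds: "Unless the subject refuses, follow-up will continue for the planned duration following the study intervention".

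Section 6.5.1.1 (item 9) and the event calendar in section 7 schedule a pain score every week of the blinded phase. Under 6.5.1.1 item 12, assignments are unsealed block by block while the trial is still running.

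**The concern.** Three features combine. First, the baseline score and the week 1-3 scores are collected but have no role in the primary test beyond the subtraction of baseline. Second, a test on change from baseline to week 4 can use only patients who have a week-4 score, unless a rule is added. Third, the plan itself expects sizeable and unequal loss.

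The consequences are a loss of precision in a 46-patient trial and, if patients with poor relief are the ones without a week-4 score, a biased treatment difference. Because the efficacy set is not defined, it could also be settled after some assignments are known.

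The fallback has a separate fault. The signed rank test is a paired or one-sample test and does not compare two independent arms.

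**Working it through.** **The plan's own figures.** 11.2 states 19 per arm, a 2.0-point difference and power 0.90, with an SD of approximately 20%. The base of that percentage, the significance level and the sidedness are not stated. Reading the SD as 2.0 points on the 0-10 scale, the two-sample t-test with 19 per arm has power 0.85 at two-sided 5% and 0.92 at one-sided 5%. Two-sided power is exactly 0.90 only at SD 1.85. So the figure can be reached only under an unstated choice. For dropout, 19 × 1.2 = 22.8, rounded up to 23. If 20% of 23 are lost, 23 × 0.8 = 18.4 per arm remain.

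**Precision.** Let σ be the common SD at both visits and ρ the correlation of week 4 with baseline (assumed; not in the documents).
- Variance of change: 2σ²(1 − ρ).
- Variance after baseline adjustment: σ²(1 − ρ²).
- Ratio: (1 + ρ)/2, which is 0.65, 0.75 and 0.85 at ρ = 0.3, 0.5 and 0.7, a cut of 35%, 25% and 15%.
- With an SD of change of 2.0, the adjusted SD is 2 × √0.65 = 1.61, 2 × √0.75 = 1.73 and 2 × √0.85 = 1.84. Two-sided power with 19 per arm is then 0.96, 0.93 and 0.90, against 0.85 unadjusted.

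**Bias, by formula.** Let d be the fraction missing in an arm, and D the mean improvement of patients with a missing score minus that of patients with an observed score. The observed difference minus the full-sample difference is −(d_active × D_active − d_sham × D_sham). Assume 10% missing on active, 30% on sham, and D = −2 where poor relief drives dropout:
- both arms: −(−0.2 + 0.6) = −0.4
- sham only: −(0 + 0.6) = −0.6
- active only: −(−0.2 − 0) = +0.2

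With 20% missing in each arm and equal D, the bias is 0.

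**Bias, by simulation** (3,000 to 4,000 trials per scenario). Assumptions: 23 per arm, SD 1.5, correlation 0.5 with baseline and 0.75-0.85 between weeks, true difference 2.0, two-sided 5%. Week 4 is missing for 13% on active and 30% on sham (about 3 and 7 of 23, so 10/46 = 22% overall). The log-odds of dropout fall by 0.6 or 1.0 per point of improvement at week 2 or week 4, and dropouts leave after week 2 or 3.

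| What drives dropout | Mean t-test estimate | t-test power |
|---|---|---|
| Unrelated to pain | 2.00 | 96% |
| Poor relief, both arms equally | 1.74-1.85 | 94-95% |
| Poor relief, sham only | 1.50-1.72 | 85-91% |
| Poor relief, active only | 2.13-2.24 | 98-99% |

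Taking the plan's allowance of 8 lost patients with equal slopes, the estimate is 2.00 if 4 are lost per arm and 1.73-1.84 if 2 are lost on active and 6 on sham. If follow-up keeps most scores (5% missing on active, 10-15% on sham), it is 1.83-1.95 (both arms), 1.74-1.91 (sham only) and 2.05-2.10 (active only). If all scores are kept, it is 2.00.

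**What a four-visit mixed model does in the same 13%/30% cases.** It gives 2.00-2.01 when dropout depends on observed week-2 relief, and about 1.84-2.08 when it depends on unobserved week-4 relief. If half of the dropouts leave before any weekly score the range is 1.76-2.12; if all do, it is 1.62-2.19, no better than baseline adjustment alone. In one case (week-2 mechanism, both arms, slope 0.6) the empirical standard errors are 0.497 for the t-test, 0.445 for baseline-adjusted regression and 0.418 for the mixed model. In variance, (0.445/0.497)² = 0.80 and (0.418/0.497)² = 0.71.

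**Feasibility at this size.** An unstructured model with Kenward-Roger degrees of freedom rejected in 5.2-5.4% of trials with no true effect (1,500 trials per case), and in 5.8% with scores rounded to integers from 0 to 10 (1,200 trials). All fits converged.

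**The case against.** The strongest reply is that the plan already covers much of this. Section 6.8 continues follow-up after the device is stopped, 6.8.2 does not treat non-compliance as leaving the study, and 11.2 commits to a dropout sensitivity analysis for either arm. Read together, most non-compliant patients should still give a week-4 score. That is a fair reading. What remains open is that objective D speaks of patients who withdraw for poor compliance, that 11.2 does not say whether scores after stopping are used, and that the sensitivity analysis has no method.

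It is also fair that an unadjusted t-test in a randomised trial is a legitimate choice. A reader might infer that the primary test is invalid, or that lack of baseline adjustment causes bias. Neither follows: with complete data the cost is precision only, and any bias comes from the missing scores.

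A reader might also infer that the plan is tilted in favour of the device, or that an exclusion of non-compliant patients is planned. The documents support neither. The one stated expectation is more loss on sham. If poor relief drives that loss, in both arms or on sham only, the estimate falls. Bias towards the device needs relief-driven loss on active only, or good responders leaving sham. In the active-only case the t-test wrongly favoured the device in 3.9-6.5% of trials with no true effect, against a nominal 2.5%; with equal or sham-only slopes, in at most 1%. No text excludes non-compliant patients from efficacy; the set is simply not defined.

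Finally, the precision gain depends on a correlation that the documents do not give. Entry at a score of 4 or more restricts the baseline range and could lower that correlation, and the floor at 0 was not modelled.

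**Conclusion.** The point stands as a choice of a weaker primary analysis when the data for a better one are already scheduled. The loss of precision is present whether or not patients drop out: roughly 15% to 35% of the variance for correlations from 0.7 to 0.3, assuming complete data and equal variances.

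The bias is conditional. Under the assumed 13%/30% loss it runs from about −0.5 to +0.2 points on a true 2.0. The negative direction, against the device, is the more likely one given objective D. It is zero if missingness is unrelated to pain, and little if follow-up under 6.8 succeeds. Dropout rates by arm and reasons for leaving are not in the documents, so these figures illustrate what could happen and do not predict this trial's result. The undefined set and the unnamed sensitivity method are gaps in specification, partly offset by 6.8 and 11.2 themselves. The signed rank fallback is wrong for a two-arm comparison whatever the dropout.

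**What to change.** In 11.2:

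1. Make the primary analysis a baseline-adjusted repeated-measures mixed model of the week 1-4 scores, with terms for baseline, arm, week, arm-by-week and baseline-by-week. Take the week-4 contrast, use small-sample degrees of freedom, and prespecify a simpler covariance in case the unstructured one does not converge. The minimum acceptable version is a regression of week 4 on arm and baseline. Report the t-test as supportive.
2. Delete the normality-conditional switch to the signed rank test, which would otherwise conflict with item 1. If a rank-based check is wanted, use the two-sample rank-sum test, as supportive only.
3. State that efficacy is analysed by assigned arm in all randomised patients who started, including scores up to week 4 that are collected after device use stops. Reconcile objective D with 6.8, 6.8.1 and 6.8.2 on whether non-compliant patients leave the study. Settle both before the first block is unblinded.
4. Name the promised dropout sensitivity analysis: a delta-adjusted tipping point or sham-based imputation covering every patient in the set, with shifts that may differ by arm and go in either direction. It is needed because the mixed model corrects only partly when dropout depends on unobserved scores, and gains nothing from patients with no weekly score.

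The cost is SAP wording, slightly more analysis work and a less simple primary model at 46 patients. No new data are needed.
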